4.0 Study Endpoints (if applicable)

The primary endpoint of this study is: quantify the antibody titers in mg/mL and opsonophagocytic antibody titer calculated as serum dilution, number of polysaccharide specific B cells, and absolute number of cells/mL induced by vaccination with PCV13.

Secondary endpoint of the study is to describe differences in gene expression of 56 genes to be determined by single cell PCR and comparing these between groups.

The primary safety endpoint of the study is measured as minimal versus moderate local side effect. Minimal side effect measured as no impairment in activity. Moderate local side effect is a side effect affecting use of the extremity for less than 24 hours.

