12.0 Data Management

Statistical Analysis Plan and Sample Size Justification for Aims 1 and 2

The primary outcomes in Aim 1 are serum antibody levels and functional antibody response measured using the OPA response at baseline and 30 days post-PVC₁₃ vaccine measured in the five groups defined in Table 1. The primary outcomes in Aim 2 are absolute number and proportion of B-cells phenotype specific to PPS₁₄, 19A, and 23F at baseline and 7 days post-PVC₁₃ vaccine measured in the same five groups. Comparisons between groups and within group between times for each aim will be evaluated using a linear

mixed model (LMM) approach. **The models will include fixed effects for participant group (65-75 RT, 35-45 RT, 65-75 DM/HTN, 65-75 healthy, and 35-45 healthy) and for time (day 0 or 30) and a random subject effect to account for repeated measures of antibody levels within participant.** Model assumptions will be checked graphically and transformations will be considered when necessary. Comparisons for each outcome between groups and within group between times will be evaluated using a series of contrasts from the LMM. **We are presenting power calculations for a range of assumptions to demonstrate that we anticipate having sufficient power to detect observed differences for all comparisons even if we fail to meet the recruitment target.** For power calculations we estimated the effect sizes for sample sizes ranging between 10 to 40 participants per group measured at 2 times at 80% and 90% power using a two-sided test assuming within subject correlation of 0.5 and Bonferroni adjusted and unadjusted significance

Figure 7: Effect sizes for different sample sizes, power, and significance

levels of $p = 0.005$ and 0.05 respectively. We will also evaluate the correlation between serum antibody levels and B cell count with OPA response across all participant groups using an LMM approach where OPA response is the dependent variable and antibody level or B-cell count is the independent variable. The model will include a random subject effect to account for repeated measures in the same subject. We anticipate good correlation (between 0.6-0.99), thus the objective is to estimate the correlation and define the level of precision around that correlation. A sample size of 200 subjects, 40 per group, provides >80% power to detect weak correlations of $r = 0.20$ and allows us to estimate a 95% confidence interval around the correlation to within ± 0.14 .

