Statistical Analysis Plan and Sample Size Justification for Aim 3

Aim 3 will examine differences in expression of TNFR markers (TACI, BCMA, and BAFF-R) using single cell qPCR on a subset of 10 participants (5 responders and 5 non-responders) from each of the 5 groups described in Aims 1 and 2 evaluated at baseline and 7 days post-vaccination. Single cell qPCR allows us to not only evaluate differences in expression between groups but also allows us to estimate the within subject and within group heterogeneity with great precision. Each participant sample provides between 40-96 viable cells that will be evaluated for gene expression at the single cell level. Relative fold-change in expression between participants who are 65-75 RT, 35-45 RT, or 65-75 DM/HTN with respect to the relevant controls will be evaluated using a linear mixed model approach. The model will include fixed effects for participant group, response status, and time and a random subject effect to account for repeated measurements resulting from individual cells from the same subject samples. Comparisons of number of gene expression between groups and within group between times will be evaluated using a series of contrasts from the LMM. For comparisons within group between responders and non-responders, a sample size of 5 responders and 5 non-responders with ≥ 40 cell level measures at 2 time points provides 80% power to detect 2.7 fold-increase or a 0.60 fold-decrease in expression using a two-sided test assuming within subject correlation of 0.5 and a Bonferroni corrected significance level (up to 10 comparisons) of $p = 0.005$. For comparisons between groups, we will have 10 subjects per group allowing us to detect even smaller fold-changes in expression.

All electronic data will be kept on the VA secure V drive or R drive and on MUSC secure Z drive that only team members will have access to.

13.0 Provisions to Monitor the Data to Ensure the Safety of Subjects (if applicable)

All adverse events (AE) will be reported and monitored through the data safety monitoring plan. The AE's will be characterized by: intensity/severity; expectedness; relatedness; frequency; outcome; treatment or action taken.

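### Aim 3 is powered at a Bonferroni level for up to 10 comparisons, but its contrasts over three markers number 15–60, and the 56-gene endpoint has no multiplicity method

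*Combined protocol and SAP*

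**What the plan says.** All of this is in the combined protocol and SAP.

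- **Section 12.0, Aim 3, power statement.** It concerns one type of comparison: "For comparisons within group between responders and non-responders, a sample size of 5 responders and 5 non-responders". With at least 40 cells per sample at two time points, the design "provides 80% power to detect 2.7 fold-increase or a 0.60 fold-decrease in expression". The calculation was made "using a two-sided test assuming within subject correlation of 0.5 and a Bonferroni corrected significance level" of 0.005, and the number allowed for is given as "Bonferroni corrected significance level (up to 10 comparisons".
- **Section 12.0, Aim 3, analysis.** Three markers are named: TACI, BCMA and BAFF-R. Three patient groups are to be compared with their relevant controls. Contrasts are also planned between groups and, within each group, between times. The mixed model has fixed effects for group, response status and time; no interaction is mentioned.
- **Section 4.0, Study Endpoints.** The secondary endpoint is to describe "differences in gene expression of 56 genes to be determined by single cell PCR" and to compare these between groups.

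The contrasts are not listed. The plan does not say whether the 10 applies per marker or overall, and it gives no multiplicity method for the analysis itself or for the gene panel.

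**The concern.** A Bonferroni divisor protects only the number of tests it was chosen for. The responder comparisons in the power statement already number 5 groups × 3 markers = 15, before any between-group or time contrast is added. A level described as corrected would then not hold the family-wise error at 5%, and the stated detectable fold-changes would belong to a looser criterion than the planned tests need.

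The three markers matter most. Section 2.0 Background argues that deficient TNFR expression could be addressed with adjuvants, and concedes that the preliminary TACI and BAFF-R finding came from very few recipients. Aim 3 follows up that finding with 10 participants per group, so its error rate should be known.

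For the panel, a reader would have no stated basis for separating real group differences from chance findings among 56 genes.

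**Working it through.** **Reproducing the plan's figure.** 0.05 / 10 = 0.005, exactly as stated. Ten independent tests at that level have a family-wise error of 1 − 0.995^10 = 4.9%. The 2.7 and 0.60 fold figures cannot be reproduced, because no standard deviation is given.

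**Counting contrasts per marker.** The plan gives no count, so these are derived from its wording.

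- Between groups: 3 if each patient group is set against one control; 10 if all pairs of five groups are compared (5 × 4 / 2).
- Time and responder status, model as written: without interactions, each effect is the same in every group, so there is 1 contrast for each. Total 3 + 1 + 1 = 5 to 10 + 1 + 1 = 12.
- Time and responder status, separate in each group, as the within-group wording implies: 5 contrasts for each. Total 3 + 5 + 5 = 13 to 10 + 5 + 5 = 20.

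**Error at 0.005.** With k independent tests and all nulls true, P(at least one false positive) = 1 − 0.995^k, and the expected number is 0.005k.

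| Family | k | P(any) | Expected |
|---|---|---|---|
| 3 markers, main effects, 3 control contrasts | 3 × 5 = 15 | 7.2% | 0.075 |
| 3 markers, main effects, all pairs | 3 × 12 = 36 | 16.5% | 0.18 |
| 3 markers, per-group contrasts, 3 control contrasts | 3 × 13 = 39 | 17.8% | 0.195 |
| 3 markers, per-group contrasts, all pairs | 3 × 20 = 60 | 26.0% | 0.30 |
| 56 genes, 3 control contrasts | 56 × 3 = 168 | 56.9% | 0.84 |
| 56 genes, all pairs | 56 × 10 = 560 | 94.0% | 2.8 |

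**Effect of correlation.** Simulating the per-group contrasts (39–60 tests) with their own correlation, and with between-marker correlation from 0 to 0.8, gave about 14–24% for the three markers. For 56 genes with 13–20 contrasts each, the chance of any false positive was 97–99% with independent genes, 83–90% at between-gene correlation 0.5, and 48–59% at 0.8. That is more contrasts than the plan assigns to the panel; it is quoted to show how strongly correlation lowers the probability. The expected number does not depend on correlation.

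**Effect on the detectable change.** The 2.7-fold figure is for 5 versus 5 within a group, so it belongs with the per-group count of 39–60. The strictest Holm step is 0.05/39 = 0.00128 or 0.05/60 = 0.00083. Using two-sided normal quantiles and 0.842 for 80% power, on the log scale:

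- k = 39: ratio (3.220 + 0.842) / (2.807 + 0.842) = 1.113; 2.7^1.113 = 3.02 and 0.60^1.113 = 0.57.
- k = 60: ratio (3.341 + 0.842) / (2.807 + 0.842) = 1.146; 2.7^1.146 = 3.12 and 0.60^1.146 = 0.56.
- Power kept at 2.7 fold: Φ(2.807 + 0.842 − 3.220) = 67% for k = 39; Φ(2.807 + 0.842 − 3.341) = 62% for k = 60.

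With about 8 degrees of freedom (an assumption, from 5 + 5 − 2), t quantiles in place of normal ones give about 3.3–3.6 fold.

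**The case against.** The strongest reply is that 0.005 is only an input to a power calculation, is never named as the analysis threshold, and is never tied to the gene panel. That is correct, so the percentages above are conditional on its being used. It does not remove the gap: if 0.005 is not the threshold, the plan fixes no threshold and no multiplicity method for Aim 3 at all.

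A second reply is that the 10 may be meant per marker, or for a narrower set. Under the model as written, 5 contrasts per marker fit within 10. The three control contrasts alone over three markers make 9 tests, with an error of 4.4%. But the paragraph also plans time and responder contrasts, and a per-marker allowance leaves nothing to correct across markers.

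A third reply is that the panel is a descriptive secondary endpoint in a study meant to characterise and explore. This has weight, and how strictly to control error there is partly a matter of judgement. The endpoint also says the genes will be compared between groups, however; if no inference is intended, the plan should say so.

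Two stronger readings are tempting. A reader might infer that false positives are close to inevitable in Aim 3. The documents do not support that. For the three markers the risk is about 7–26%, and a figure above 90% needs ten or more contrasts on each of 56 genes, tested at 0.005, with weak correlation between genes. A reader might also extend the point to Aims 1 and 2, where the same 0.005 appears. That section never says which comparisons the level covers. Even if 10 group pairs plus 5 time contrasts are counted per outcome, 15 tests give 7.2%. That is too slight, and rests too much on inference, to press.

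**Conclusion.** The point holds for Aim 3. An allowance of 10 comparisons is smaller than the set of tests the paragraph describes over its three markers, on either reading of the model. With 0.005 as the threshold, independent tests and all nulls true, the family-wise error would be about 7–17% (15–36 tests) or 18–26% (39–60 tests). Which range applies depends on whether the within-group contrasts imply interactions that the stated model omits; the section needs to settle this.

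For the 56-gene endpoint, the finding is that a multiplicity method is absent, not that a stated one fails. If 0.005 were carried over, three control contrasts per gene would give about 0.8 expected false positives (57% chance of any), and all ten pairs 2.8 (94% if independent, lower if genes are correlated). The section 4.0 wording supports only between-group contrasts for the panel, so larger counts that add time and responder contrasts are not documented.

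The adjuvant rationale rests on the TNFR markers, so the three-marker range is the one that bears on it. No decision rule in the plan depends on these p-values.

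**What to change.** In section 12.0, Aim 3:

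1. List the contrasts, and state whether time and responder effects are estimated separately in each group. If so, add the interactions to the model.
2. Apply Holm at 5% across the declared contrasts × 3 markers.
3. For the 56-gene panel, control the false discovery rate at 5% with Benjamini-Hochberg across genes × between-group contrasts.
4. Replace the allowance of up to 10 comparisons with the actual number, and restate the detectable fold-change, giving the standard deviation and degrees of freedom used.

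No new data are needed. The cost is fewer genes declared different and less power for the markers. At the strictest Holm step for 39–60 tests, the detectable increase rises from 2.7 to roughly 3.0–3.1 fold (0.60 moves to about 0.57–0.56), or power at 2.7 fold falls from 80% to about 62–67%. These are normal approximations scaled from the plan's own figures and would be worse with few degrees of freedom. Because 2.7 and 0.60 are not reciprocals (1/2.7 = 0.37), they are indicative only. Declaring fewer contrasts reduces the cost.

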14.0 Withdrawal of Subjects (if applicable)

Subjects will only be withdrawn from the study for failure to appear at day 7 and day 30, the 2nd and 3rd visit of the study, at which times crucial blood samples are to be obtained. This may occur

voluntarily at the participant's discretion or due to unforeseen circumstances. Should this occur, no further study visits will be requested and no further visit payments will be made.

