Monitoring will be performed at each study visit by the study coordinator and/or P.I. and will occur at the Ralph H. Johnson VA Medical Center and MUSC and all AEs will be recorded on an event form with physician/nurses/coordinator notes attached. These will be reviewed by the safety monitoring committee. The safety monitoring committee will include board certified Infectious Diseases specialists. Meetings will occur on a quarterly basis. [name], the P.I. will arrange for the meetings quarterly, make all materials available for review by the committee and be ultimately responsible for the meetings.

The study endpoints will be reporting and assessing safety of the vaccination and blood draw procedures and to ensure that these procedures are well within the acceptable complication risk associated with vaccination and blood draws.

All serious, unexpected, AND related adverse events will be reported to the MUSC IRB within 10 working days of learning of the event.

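### The withdrawal rule leaves open whether one missed visit or both end follow-up; if one is enough, missing the day-7 draw forfeits the day-30 primary outcome

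*Combined protocol and SAP*

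**What the plan says.** Section 14.0 sets one ground for withdrawal: "Subjects will only be withdrawn from the study for failure to appear at day 7 and day 30". It numbers these as visits two and three, and the reason given is that important blood is drawn at those times. The consequence is "Should this occur, no further study visits will be requested and no further visit payments will be made". The section does not say whether one absence is enough, and it does not say that results already obtained are removed.

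The two visits feed different outcomes. In Section 12.0, "The primary outcomes in Aim 1 are serum antibody levels and functional antibody response measured using the OPA response at baseline and 30 days" after PCV13. For the B cells, "The primary outcomes in Aim 2 are absolute number and proportion of B-cells phenotype specific to" the three polysaccharides, at baseline and day 7. The Aim 3 single-cell expression work also uses baseline and day 7. Section 10.0 assigns the day 0, day 30 and yearly samples to antibody and OPA assays, and the day 0 and day 7 samples to flow cytometry.

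The Aim 1 model has a "random subject effect to account for repeated measures of antibody levels within participant". No missing-data rule or analysis set is stated. On safety, Section 13.0 says "Monitoring will be performed at each study visit by the study coordinator and/or P.I", and Tables 1 to 3 in Section 10.0 list side-effect reports at the follow-up visits.

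**The concern.** A missed B-cell draw is no scientific reason to forgo the antibody draw about three weeks later. The samples are separate, and a mixed model can use participants with an incomplete series. A rule that ends all visits therefore creates missing data that the analysis does not require.

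What is lost depends on how the rule is read. If either absence triggers it, the loss falls on the Aim 1 primary outcome. If both are needed, it falls on the yearly samples, which are meant to show how long the response lasts, and on the remaining scheduled side-effect reports. Local side effects are the primary safety endpoint in Section 4.0, and a Group 3 or 4 participant who missed both visits has given no scheduled post-vaccination report.

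Because the trigger is also hard to map onto the transplant and Group 5 schedules, it could be applied differently across the groups being compared.

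**Working it through.** **The plan's own figures.** Section 12.0 gives more than 80% power for r = 0.20 and a 95% interval within ±0.14 at N = 200.
- Power = Φ(atanh(0.20)·√197 − 1.96) = Φ(0.2027 × 14.036 − 1.96) = Φ(0.885) = 81.2%.
- Half-width at r = 0: tanh(1.96/√197) = 0.139.
- Ten pairwise comparisons of five groups: 0.05/10 = 0.005.

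All three reproduce. None depends on the withdrawal rule. A withdrawn participant's day-0 values can still enter the correlation model, so I do not carry the loss into it.

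**Day-30 loss under each reading.** Let m be the chance of missing a given visit. The plan gives no value; I take 5% to 20%, independent between visits.
- Both visits needed: the share withdrawn is m². All of them missed day 30 anyway, so day-30 loss stays at m.
- Either visit enough: day-30 loss is 1 − (1 − m)².
- Extra loss from the rule: 1 − (1 − m)² − m = m(1 − m).

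| m | withdrawn, both needed | day-30 loss, both needed | day-30 loss, either enough | extra loss | extra per 40 |
|---|---|---|---|---|---|
| 5% | 0.25% | 5% | 9.75% | 4.75% | 1.9 |
| 10% | 1% | 10% | 19% | 9% | 3.6 |
| 15% | 2.25% | 15% | 27.75% | 12.75% | 5.1 |
| 20% | 4% | 20% | 36% | 16% | 6.4 |

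If people who miss day 7 also tend to miss day 30, the extra loss is smaller and the share withdrawn under the literal reading is larger.

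**Effect on a group contrast, either reading, base of 40 per group.** In SD units, the difference detectable with 80% power at α = 0.005 is (2.807 + 0.842)·√(2/40) = 0.816. With within-subject correlation 0.5, the SD of a change is √(2(1 − 0.5)) = 1, so the same figure serves for a difference in change. Taking off only the extra loss leaves about 38, 36 or 34 per group at m = 5%, 10% or 20%. Power for 0.816 SD is then 77.3%, 74.4% or 71.1%.

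**Base of 55 per group.** Section 6.0 gives 275 subjects, and 275/5 = 55. The margin down to 40 is 1 − 40/55 = 27.3%. Under the either reading, 55(1 − m)² leaves 49.6, 44.6, 39.7 and 35.2 at the four rates, so 40 is breached when m exceeds 1 − √(40/55) = 14.7%. Under the literal reading, 55(1 − m) leaves 44 even at m = 20%.

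**Does the trigger fit the schedules in Section 10.0?**
- First ten in Group 1: days 0, 5, 7, 10, 30. The second and third visits are days 5 and 7; day 30 is the fifth.
- Remaining Group 1 and Group 2: the second visit is on day 5, 7 or 10, so there may be no day 7 visit.
- Groups 3 and 4: days 0, 7, 30. The rule fits.
- Group 5: PCV13 on day 366, then days 373 and 396, which are 7 and 30 days later. In Table 3 the second visit is the PCV13 visit when PPV23 is given first.

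**The case against.** The strongest reply is textual. The sentence limits withdrawal to a single ground and joins the visits with a conjunction, so literally both must be missed. A participant absent only at day 7 stays in and can give the day-30 sample. That stands. A reader might infer that the plan throws away the day-30 result of anyone who missed the B-cell draw. The documents do not support this: the literal wording points the other way, and even under the either reading the sample is not requested, rather than a result being deleted.

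Other replies also stand in part:
- Day 7 serves Aim 3 as well as Aim 2, and B-cell numbers are part of the primary endpoint in Section 4.0. Treating it as an important visit is consistent with the plan.
- Withdrawal does not end all safety contact. Section 15.0 gives each volunteer a telephone number for reactions beyond local ones. What ends is scheduled reporting.
- The 71% to 77% power figures need the either reading, assumed miss rates and 40 per group. With 55 per group, 40 is still exceeded at 10% missed. The documents are not uniform here: Table 2 counts Group 1 subjects to 55, while the text of Section 10.0 stops at 40.
- A reader might infer biased group contrasts because frailer transplant recipients miss more visits. Section 14.0 attributes absence only to participant discretion or unforeseen circumstances. Differential loss is possible but not shown.
- Yearly samples are outside the stated Aim 1 model, whose time effect is day 0 or 30.

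These replies remove any claim of demonstrated primary-outcome loss. They do not defend the rule, which saves little and can only reduce data.

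**Conclusion.** The point holds as an unclear and unnecessary rule. On the literal reading the cost is small: no extra day-30 loss, and the yearly antibody and OPA samples and remaining scheduled side-effect reports of 0.25% to 4% of participants. On the either reading, which the stated rationale allows, the rule forfeits a further 4.75% to 16% of day-30 primary outcomes, about 2 to 6 of every 40 per group. Enrolling 55 per group absorbs this until roughly 15% miss each visit. All these sizes rest on assumed, independent miss rates of 5% to 20%.

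The mismatch with the visit schedules needs no assumption. The trigger fits Groups 3 and 4 but not the first ten in Group 1, any transplant recipient drawn on day 5 or 10, or Group 5. The documents do not show an underpowered or biased trial on this account. This is a cheap improvement worth making.

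**What to change.** Replace the rule in Section 14.0 with three statements:
1. A missed visit makes only that visit's sample missing. The participant is still asked to attend day 30 and the yearly visits unless consent is withdrawn.
2. All available samples enter the mixed model, and Section 12.0 says how missing values are handled.
3. The B-cell visit and the antibody visit are defined by days since PCV13, separately for each group's schedule, so that Sections 10.0 and 14.0 agree.

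The cost is protocol wording and visit payments for the few participants retained. Vaccination and clinical care are untouched.
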